9.3 Sample Size Justification

We calculated the trial's required sample size to achieve sufficient power to detect treatment group differences in FMD at Week 12. Using the effect size of *Beating the Blues* on FMD in our pilot trial, and assuming a power level of 0.80 with a Type I error of 0.05, we will need 88 participants (44 per arm) to detect an absolute difference in FMD of 1.7% at Week 12. This would be a clinically meaningful difference, as a 1.0% higher baseline FMD predicted a 6% lower risk of CVD events over five years in MESA (123, 124). We will increase the sample size to 110 (55 per group) to account for a conservative attrition rate of 20%. For the secondary outcomes of FMD (Week 24) and circulating IL-6, hsCRP, and D-dimer levels (Weeks 12 and 24), we will be able to detect effect sizes as small as 0.61 standard deviations.

9.4 Criteria for Stopping the Study

No early stopping rule will be implemented.

9.5 Analysis Datasets

Datasets	Definition
Intention-to-treat (ITT)	This will comprise all patients who meet the eligibility criteria and are randomized onto the study irrespective of their compliance to the planned course of treatment.
Per Protocol Set	This will comprise all UC patients and BtB participants who finish at least 6 out of 8 sessions.
Safety	This will comprise the BtB patients that attend at least one session of treatment.

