3.4 Beating the Blues Treatment Sessions and Usual Care

3.4.1 Beating the Blues

To minimize treatment barriers, attrition, and subject burden, the BtB treatment sessions will occur in private at [name] laboratory, the ICRC, the Infectious Diseases Research Clinic at Eskenazi Health Hospital, or a location selected by the patient where s/he can access a computer with internet, such as the patient's home, the patient's work, a family member's/friend's home, or a public library. The location will be chosen by the participant. To help maintain privacy, patients will be provided with ear bud headphones if they plan to complete BtB sessions at remote locations and do not already own a pair of headphones that they would rather use. We will also tell patients that, if they choose to complete BtB session where others are present, these other people (e.g., family member or friend) may realize that they are completing a treatment for depression. It will be up to each patient to decide if the available remote locations provide sufficient privacy. Up to 8 sessions will be performed between the Second Entry Visit and the Week 12 Visit. The PHQ-9 questionnaire will be administered at each of the Weekly BtB Sessions. No physiologic or biologic assessments will be performed during these sessions. The participants need not be fasting for these sessions.

At each in-person BtB session, a research assistant trained in the use of this intervention will first collect homework and will start the appropriate session on a computer. The patient will then work through the session alone at his/her own pace. At the end of the session, the research assistant will give the patient the printed homework assignment and will schedule the next session.

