3.4.2 Usual Care

This arm was modeled after the IMPACT trial's control group (48). Patients randomized to the Usual Care group will be informed of their depression diagnosis and will be encouraged to follow-up with their primary care or HIV provider. There will be no formal interaction with the participants between the Second Entry Visit and the Week 12 Visit. However, the participants will be encouraged to contact the study team for any changes in their condition.

Our team will also send their primary provider a letter indicating that their patient has a depressive disorder and was randomized to usual care and will include a list of local mental health services. Although feedback to patients and providers could result in treatment that would not have occurred naturally, studies have shown that informational support alone is unlikely to improve depression outcomes (125). In our pilot study which used this control group, only 14% of Usual Care patients had >50% reduction in symptoms versus 43% of *Beating the Blues* patients. There will be no restrictions on the care that can be received, although we will assess changes in care during the trial.

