9.10 Analysis Plan for the Primary Objective

To test our primary hypothesis, an analysis of covariance (ANCOVA) will be performed to test for treatment group differences in Week 12 FMD adjusted for baseline FMD using the intent-to-treat set. Statistical significance will be considered if two-sided p-value <0.05. This analysis will be also repeated using the per-protocol set.

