9.11 Analysis Plan for Secondary Objectives

Both unadjusted comparisons and adjusted comparisons between UC and BtB will be performed for secondary outcomes defined in 1.2.1-1.2.3. For adjusted comparisons, multiple linear regression models will be constructed to include treatment group, baseline characteristics [demographics, SCL-20 scores, tobacco/exercise/adherence questionnaire results, ART drugs/regimens (including efavirenz (142-144)), antidepressant use, co-morbidities, CD4 cell counts, and HIV-1 RNA levels], and time-varying characteristics (changes in SCL-20 scores, questionnaire results, CD4 cell counts, ART drugs/regimens, HIV-1 RNA levels) to determine their effects on the outcomes. Pearson and Spearman correlation coefficients will be estimated for FMD, IL-6, hsCRP, D-dimer, circulating EPCs/ECFCs levels, and markers of monocyte activation (CD14+CD16+ cell proportions and sCD14/sCD163) with PHQ-9 and SCL-20 scores at baseline. These analyses will be performed for both the intent-to-treat set and the per-protocol set. Dose-response relationships between 12- and 24-week FMD and the number of BtB sessions, which have a range from 0 to 8, will be explored.

Safety assessments will be performed using the safety dataset. HIV-1 RNA levels and CD4 cell counts of the BtB arm during the trial will be summarized and compared to the UC arm.

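### The per-protocol set filters only the BtB arm, on session completion after randomization, so the per-protocol comparisons in 9.10 and 9.11 are open to selection bias of unknown sign and size; the primary ITT result is not affected

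*Combined protocol and SAP*

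**What the plan says.** Section 9.5 gives the per-protocol set in one sentence: "This will comprise all UC patients and BtB participants who finish at least 6 out of 8 sessions". No condition is placed on UC. The ITT set in the same table is everyone eligible and "randomized onto the study irrespective of their compliance to the planned course of treatment".

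The selecting variable arises after randomization, which takes place at the Second Entry Visit. Section 3.4.1 states: "Up to 8 sessions will be performed between the Second Entry Visit and the Week 12 Visit". UC has no sessions and, under 3.4.2, no formal contact in that interval.

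Section 9.10 makes the primary analysis an ANCOVA for "treatment group differences in Week 12 FMD adjusted for baseline FMD using the intent-to-treat set", and adds: "This analysis will be also repeated using the per-protocol set". Section 9.11 says of the secondary outcomes: "These analyses will be performed for both the intent-to-treat set and the per-protocol set". It also plans an exploratory dose-response of 12- and 24-week FMD on number of sessions (0 to 8).

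Neither section describes weighting, a complier analysis or any limit on interpreting the per-protocol result. Section 9.8 will tabulate compliance in the BtB arm, but no expected completion rate is given. Nothing is reported on how completers and non-completers differ in FMD.

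**The concern.** Randomization makes the two arms comparable as whole groups. Removing BtB participants who finish fewer than 6 sessions leaves a self-selected part of one arm beside all of the other. UC contains the same kind of people, those who would have stopped early had they been offered BtB, but they cannot be identified and stay in. If persistence with a self-paced programme and its homework is related to Week 12 FMD beyond baseline FMD, the arms differ even when BtB does nothing.

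That relation is plausible on the protocol's own terms. Section 3.6 says that tobacco, alcohol, diet and medications affect vasomotor function, and 3.7 treats smoking, exercise and medication adherence as possible behavioural pathways to the outcomes. Adjusting for baseline FMD, the only covariate in 9.10, does not remove selection on later behaviour.

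What is at stake is the supportive evidence. If the ITT result is null and the per-protocol result is nominally significant, the plan has no rule against reading the second as efficacy among those who completed treatment.

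**Working it through.** **1. The plan's own figure.** Section 9.3 targets 1.7 FMD points with power 0.80 and two-sided 5% error. The pilot table in 2.3.5 gives d = 0.61, so the implied SD is 1.7/0.61 = 2.79. The pooled adjusted pilot SD agrees: √[(12 × 2.86² + 15 × 2.72²)/27] = 2.78. A two-sample t-test at d = 0.61 needs 43.17, rounded up to 44 per arm, or 88 in total, and 88/0.80 = 110. The plan's sample size reproduces, and the per-protocol rule does not affect it.

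**2. Inputs for the illustration.**
- From the documents: SD 2.79; 44 analysed per arm; two-sided 5%.
- Assumed: the completion rate p (at least 6 sessions), and r, the correlation between a normally distributed completion propensity and baseline-adjusted Week 12 FMD.
- True BtB effect: zero.

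**3. Shift in the per-protocol difference.** The mean of the upper fraction p of a standard normal is φ(z)/p, where z is its (1 − p) quantile. The shift in SD units is therefore r × φ(z)/p.
- p = 0.6: φ(z)/p = 0.386/0.6 = 0.644.
- p = 0.8: φ(z)/p = 0.280/0.8 = 0.350.

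**4. Rejection rate under no effect.** With 44 UC and 44p BtB participants, the standard error in SD units is √(1/44 + 1/(44p)). This is 0.246 at p = 0.6 and 0.226 at p = 0.8. Shift divided by standard error is the noncentrality of the t-test.

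| p | r | Shift (SD) | Shift (points, × 2.79) | Share of 1.7 | Noncentrality | Two-sided rejection |
|---|---|---|---|---|---|---|
| 0.6 | ±0.2 | ±0.129 | ±0.36 | 21% | 0.52 | 8.1% |
| 0.6 | ±0.3 | ±0.193 | ±0.54 | 32% | 0.78 | 12.1% |
| 0.8 | ±0.1 | ±0.035 | ±0.10 | 6% | 0.15 | 5.3% |
| 0.8 | ±0.2 | ±0.070 | ±0.20 | 11% | 0.31 | 6.1% |
| 0.8 | ±0.3 | ±0.105 | ±0.29 | 17% | 0.46 | 7.4% |
| any | 0 | 0 | 0 | 0 | 0 | 5.0% |

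Simulation of 20,000 null trials per scenario agrees within simulation error.

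**5. A second route.** Let g be the difference in untreated Week 12 FMD between would-be completers and non-completers. The shift is (1 − p) × g. With g assumed at 0.7 to 1.4 points and p at 50% to 90%, it runs from 0.1 × 0.7 = 0.07 to 0.5 × 1.4 = 0.70 points, or 4% to 41% of 1.7. Rejection runs from 5.2% to 18.6% with 55 UC and 55p BtB participants. With g = −1.4 the sign reverses; with g = 0 the shift vanishes. In the same simulated trials the ITT ANCOVA rejected 4.5% to 5.7% of the time.

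**6. The alternative.** The complier estimate is the ITT difference divided by the between-arm difference in treatment received. UC receives no BtB sessions, so with 6 or more sessions as treatment received the divisor is p. In null simulations it rejected 4.0% to 4.7% of the time. Its price is precision. The ITT standard error is 2.79 × √(2/44) = 0.59 points, so the complier standard error is about 0.59/0.6 = 0.99 points at 60% completion and 0.59/0.8 = 0.74 at 80%. The per-protocol values are 2.79 × 0.246 = 0.69 and 2.79 × 0.226 = 0.63, narrower but around a quantity that randomization does not protect.

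**The case against.** The per-protocol analysis is a repeat of an ITT primary test, and no section gives it priority. Section 10.1 describes the trial as one of mechanisms, not superiority. This stands, and it limits the consequence to supportive analyses.

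A reader might infer that the bias favours BtB. Completers may well have better prognosis, and then it would. But no section links completion to FMD; a negative r gives the mirror image and r = 0 gives nothing.

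A reader might add that UC participants who start other care, or anyone taking a prohibited drug, make the set still more uneven. The documents do not support that. In UC "There will be no restrictions on the care that can be received", so other care is no deviation. A BtB completer who does the same also stays in. Needing a prohibited drug is a discontinuation criterion in both arms (8.0). If other care improves FMD, its use in UC would pull against BtB. Only the session rule differs by arm.

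Nor is the per-protocol result the plan's only look at BtB as taken, since 9.11 also explores dose-response by sessions. That analysis rests on the same self-selected session counts and is no safeguard.

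The adjusted models in 9.11 include SCL-20, smoking, exercise, adherence, antidepressant use and co-morbidities. They should reduce the selection for secondary outcomes. They cannot be relied on to remove it, and they do not apply to 9.10.

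The 60% scenario is on the pessimistic side: 0.6 × 44 = 26.4, so if everyone lost to follow-up is also a non-completer, only 26.4/55 = 48% of those randomized would have completed. At 80% completion the effect is modest.

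Finally, the complier analysis has its own assumption. If 1 to 5 sessions have an effect, the 6-session version violates it. That is a reason to state the assumption and run both versions, not to keep an unprotected comparison with a p-value.

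**Conclusion.** The point holds for the per-protocol comparisons in 9.10 and 9.11. Selection in one arm on behaviour after randomization removes the protection of randomization, and the plan does nothing about it. Sign and size are not fixed by the documents. The figures in the table rest on an assumed completion rate, an assumed r, a normal completion propensity, an SD of 2.79 and no true effect. Within those ranges the shift goes from nil to about a third of the 1.7-point design difference in either direction, and the nominal 5% test rejects up to about 12% of the time.

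The primary ITT conclusion is untouched, and it would be wrong to infer that the trial's main result is compromised. This is an inexpensive improvement to the supportive analyses that should be made.

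**What to change.** In 9.10 and 9.11, estimate the effect of receiving BtB as a complier average causal effect in all randomized participants, with assignment as the instrument and the same baseline value as covariate. Fit it twice: once with 6 or more sessions as treatment received, and once with number of sessions (0 to 8). UC has 0 BtB sessions in both.

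State the limits in the plan. The interval is wider than that of the ITT analysis. The method assumes that assignment acts on the outcome only through the sessions, which the 6-session version violates if fewer sessions have an effect. The 0-to-8 version relaxes this but, as a linear model, summarises an effect per session.

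Keep the current per-protocol comparison only as descriptive, labelled non-randomized, without a p-value or efficacy conclusion. Put the same caution on the dose-response exploration in 9.11.

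The cost is plan wording and one further model in two versions. Session counts are already needed for 9.5, 9.8 and 9.11, so no new data are required and the sample size is unchanged.

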1.2 Secondary Objectives

1.2.1 To compare 24-week changes in FMD between those undergoing depression treatment using BtB vs those receiving UC.

1.2.2 To compare 12 and 24-week changes in circulating levels of IL-6, hsCRP, D-dimer, fasting lipid profiles (total cholesterol, HDL-C, LDL-C, triglycerides), insulin resistance estimated using HOMA-IR, systolic and diastolic blood pressures, body mass indices (BMI), circulating EPC/ECFC levels, and circulating markers of monocyte activation (CD14+CD16+ cell proportions and sCD14/sCD163) between those undergoing depression treatment using BtB vs those receiving UC.

1.2.3 To compare 12 and 24-week changes in PHQ-9 scores and SCL-20 scores between those undergoing depression treatment using BtB vs those receiving UC.

1.2.4 To correlate FMD, IL-6, hsCRP, D-dimer, circulating EPCs/ECFCs, and markers of monocyte activation (CD14+CD16+ cell proportions and sCD14/sCD163) levels with PHQ-9 and SCL-20 scores at baseline.

1.2.5 To assess the safety, HIV-1 RNA levels, and CD4 cell counts of the BtB program in HIV-infected adults.

1.2.6 To explore the relationships between genetic markers with FMD, PHQ-9, SCL-20 scores at baseline and with response to depression treatment with BtB.

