2.0 HYPOTHESES, BACKGROUND, AND INTRODUCTION

2.1 Hypotheses

2.1.1 Treatment with BtB will improve FMD, increase circulating EPC/ECFC levels, and reduce circulating levels of IL-6, hsCRP, D-dimer, and markers of monocyte activation (CD14+CD16+ cell proportions and sCD14/sCD163) at both 12 and 24 weeks when compared to UC.

2.1.2 Treatment with BtB will improve PHQ-9 and SCL-20 scores at both 12 and 24 weeks when compared to UC.

2.1.3 Treatment with BtB will be safely tolerated and have no effects on HIV-1 RNA suppression or CD4 cell counts.

2.1.4 Genetic variation is associated with endothelial function, depression severity, and response to depression treatment.

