6.0 CLINICAL AND LABORATORY EVALUATIONS

6.1 Schedule of Events

Evaluation	Screening Visit	First Entry Visit (within 15 days of Screening)	Second Entry Visit #2 (within 30 days after Screening)	Weekly BtB Sessions for the intervention group (8 in total)	Week 12 Visit (for both groups; 84-105 days after Second Entry Visit)	Week 24/Closeout Visit (for both groups; 168-189 days after Second Entry Visit)
Informed Consent	X					
Documentation of HIV Status	X					
Medical/Psychiatric History	X					
Medication/Supplement Use History	X					
Updated Psychiatric Management			X		X	X
Concomitant/Updated Medications			X		X	X
PHQ-9 Assessment	X	X	X	X	X	X
Signs & Symptoms	X		X		X	X
Diagnoses/Updated Diagnoses	X		X		X	X
Height		X				
Weight		X	X		X	X
Vital Signs	X	X	X		X	X
Brief Physical Examination	X	X	X		X	X
Urine Pregnancy Test	X	X	X		X	X
Randomization			X			
Serum chemistries/glucose, total cholesterol (non-fasting)	X					
Hematology, hemoglobin A1c	X					
HIV-1 RNA level	X		X		X	X
CD4 cell count			X		X	X
Whole blood for ECFCs and monocyte subsets		X	X		X	X
DNA sampling			X			
Beating the Blues Behavioral Intervention				X		
Questionnaires			X		X	X
FMD/NTGMD		X	X		X	X
Frozen Serum for Batched Testing of Inflammatory/Coagulation Markers, Metabolic Markers		X	X		X	X
Frozen Plasma, Serum, and Urine for Future Studies		X	X		X	X

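### The safety set contains only BtB attendees, so adverse events would be analysed without the randomized usual-care arm although both arms supply the data

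*Combined protocol and SAP*

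**What the plan says.** Section 9.5 defines three analysis sets. The per-protocol set expressly includes UC patients. The safety set does not: "This will comprise the BtB patients that attend at least one session of treatment".

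Section 9.11 then states: "Safety assessments will be performed using the safety dataset". Its general between-arm comparisons are limited by objective: "Both unadjusted comparisons and adjusted comparisons between UC and BtB will be performed for secondary outcomes defined in 1.2.1-1.2.3". Safety is objective 1.2.5 in Section 1.2: "To assess the safety, HIV-1 RNA levels, and CD4 cell counts of the BtB program in HIV-infected adults". One further sentence in 9.11 brings UC in for two laboratory measures: "HIV-1 RNA levels and CD4 cell counts of the BtB arm during the trial will be summarized and compared to the UC arm". It names no analysis population.

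The related hypothesis, 2.1.3, reads: "Treatment with BtB will be safely tolerated and have no effects on HIV-1 RNA suppression or CD4 cell counts".

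**The concern.** Taken together, 9.5 and 9.11 leave no UC participant in the only population named for safety, and no other section specifies an adverse event analysis by arm. The first part of hypothesis 2.1.3, safe tolerability, would then rest on BtB event counts alone. Intercurrent events can be expected in treated adults with HIV and depression whatever the arm, and counts from one arm cannot separate those from events linked to the intervention. A concurrent randomized control group would supply the background rate, and its data are already being collected.

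The set also omits randomized BtB participants who attend nothing. Section 9.11 allows for them when it describes "the number of BtB sessions, which have a range from 0 to 8". An event between randomization and the first session in such a participant would not be counted.

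**Working it through.** **1. Who is in the set.** Section 9.3 gives 110 randomized, 55 per arm. Under 9.5 the set holds at most 55 BtB and 0 UC participants: 55/110 = 50% at most, and fewer if any BtB participant attends no session. No between-arm difference can be estimated from it.

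**2. Arm sizes.** Section 9.3 states 88 evaluable (44 per arm), inflated to 110. With an effect of 0.61 SD, power 0.80 and two-sided alpha 0.05, the t-test calculation gives 43.17, that is 44 per arm or 88 in all. Then 88/(1 − 0.20) = 110. The plan's figures reproduce, and 55 and 44 per arm are used below.

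**3. Are the data collected in both arms?**
- Section 6.1 schedules signs and symptoms and updated diagnoses at Weeks 12 and 24. The first of these columns is headed "Week 12 Visit (for both groups; 84-105 days after Second Entry Visit"), and the Week 24 column is likewise for both groups.
- Section 6.2.5.6 requires signs and symptoms of every grade on CRFs, without restriction by arm.
- Section 7.0 puts all SAEs on CRFs. It justifies recording Grade 3 and 4 toxicities by uncertainty about the effects of depression therapy or of its absence. The second half of that question concerns UC.

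**4. Is a by-arm analysis given elsewhere?** Section 9.1 promises summary statistics for side effects but names no population and no comparison. Section 10.6 provides six-monthly reports of all adverse events to a review panel; that is monitoring. Neither fills the gap.

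**5. What a by-arm table would deliver.** The documents give no event rate, so equal rates of about 5–20% in both arms are assumed. With Wilson limits *l* and *u* for an observed proportion *p*, and equal counts in both arms, the Newcombe 95% CI for the difference has half-width √[(p − l)² + (u − p)²].

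| Per arm | Events in each arm | p (%) | Wilson l to u (%) | Half-width (points) |
|---|---|---|---|---|
| 55 | 3 | 5.5 | 1.9 to 14.9 | ±10.1 |
| 55 | 6 | 10.9 | 5.1 to 21.8 | ±12.4 |
| 55 | 11 | 20.0 | 11.6 to 32.4 | ±15.0 |
| 44 | 2 | 4.5 | 1.3 to 15.1 | ±11.1 |
| 44 | 5 | 11.4 | 4.9 to 24.0 | ±14.2 |
| 44 | 9 | 20.5 | 11.1 to 34.5 | ±16.8 |

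For example, 6 of 55 in each arm: √[(10.91 − 5.10)² + (21.83 − 10.91)²] = 12.4. The 44-per-arm rows apply the 20% attrition in 9.3 (55 × 0.80 = 44).

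For CD4 or another continuous measure, the unadjusted 95% CI half-width is t × √(2/n) SD: 1.98 × √(2/55) = 0.38 SD, and 1.99 × √(2/44) = 0.42 SD.

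**The case against.** The strongest reply is that the plan does what it set out to do. Objectives 1.2.1–1.2.3 call for a comparison of BtB with UC, whereas 1.2.5 speaks of the safety of the BtB program. Hypotheses 2.1.1 and 2.1.2 refer to UC, and 2.1.3 does not. An exposed-only set serves an exposed-only objective. This stands to the extent that the text does not contradict itself and a BtB-only summary may have been meant. Intent does not supply a background rate, however.

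Second, the causal part of 2.1.3 is already compared with UC through HIV-1 RNA and CD4. That also stands. The gap covers adverse events, SAEs and symptoms; for RNA and CD4 the population needs naming, since UC lies outside the only safety set defined. It is also true that 9.11 refers to safety assessments without naming adverse events. Reading it that way follows from 1.2.5 and Section 7.0, and no other population is offered for them.

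Third, UC events are still recorded and reviewed, and 9.1 permits additional exploratory analyses. Nothing therefore prevents a by-arm table, but nothing plans one.

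Fourth, this is a single-centre pilot of a program for which Section 10.2.3 states no known risks, and the comparison would be imprecise. Both points limit the weight of the issue. Safety is nonetheless a stated objective, and Section 2.4 calls this the first test of the program in an HIV-infected population.

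Last, requiring one attended session is a recognised exposure-based choice, and all UC plus BtB attendees would also restore a control group. Using all randomized participants is preferred because it keeps the randomized comparison intact; the attendee set remains useful beside it.

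**Conclusion.** The concern holds. As written, the safety set excludes all 55 UC participants and any BtB participant without a session, and no section provides an adverse event analysis by arm. The safe-tolerability claim would have no background rate even though both arms supply the data. This is a weak analysis choice, not an internal contradiction, and it should be fixed. The primary ITT ANCOVA and the sample size are unaffected.

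The effect on the safety conclusion cannot be sized without an event rate. The precision figures rest on assumed equal rates of about 5–20% and either no attrition or the 20% in 9.3. On that basis a by-arm table would be descriptive and could not exclude a moderate difference.

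**What to change.** 1. In 9.5, define the safety set as all randomized participants, analysed by randomized arm. Keep BtB participants with at least one session as a supplementary listing.
2. Report Grade 3 and 4 events, SAEs, HIV-1 RNA and CD4 by arm, with differences and 95% CIs. Base the comparison on information collected at Weeks 12 and 24, with the same look-back period in both arms and the number attending shown. This matters because BtB has up to 8 extra contacts with a PHQ-9 at each (Section 5.1), while UC has no formal contact before Week 12 (Section 3.4.2).
3. List separately, by arm, anything known only through other contact: PHQ-9 item 9 responses at BtB sessions (which have no UC counterpart), UC self-reports between visits, and SAEs in participants who miss a visit or leave before it.
4. Name this set in both safety sentences of 9.11.

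The cost is SAP wording and table shells, with no new data or visits. There are two trade-offs. Including BtB participants with no session dilutes any effect specific to exposure, which is why the attendee listing stays. A comparison limited to the common visits omits events in non-attenders, which is why the all-source listing is needed.
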